## **Response Criteria:**

Protocol name: Phase II Neoadjuvant trial of Nivolumab in Combination with HF10 Oncolytic Viral Therapy in Resectable Stage IIIB, IIIC, IVM1a Melanoma (Neo-NivoHF10) Version Date: 22JUL2019 Principal Investigator: [name]

	Neither sufficient shrinkage to qualify for PR nor sufficient increase to qualify for PD, taking as reference the smallest sum LD since the treatment started

	Evaluation of non-target lesions
Complete Response (CR)	Disappearance of all non-target lesions
Stable Disease (SD)	Persistence of one or more non-target lesion(s)
Progressive Disease (PD)	Appearance of one or more new lesions and/or unequivocal progression of existing non-target lesions

#### **Evaluation of Best Overall Response**

The best overall response is the best response observed until progression/recurrence and is determined as indicated in the table below:

Target Lesions	Non-Target Lesions	Evaluation of New Lesions	Best Overall Response
CR	CR	No	CR
CR	SD	No	PR
PR	Non-PD	No	PR
SD	Non-PD	No	SD
PD	Any	Yes or No	PD
Any	PD	Yes or No	PD
Any	Any	Yes	PD

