#### **1.2.2** Assess overall survival

Endpoint: patients will be followed for survival for one year after completion of adjuvant nivolumab.

**1.2.3** Assess the response of tumors prior to surgery based on RECIST 1.1

Endpoint: patients will be assessed radiographically with CT or MRI scan or assessed clinically.

**1.2.4** Assess complete surgical resection

Endpoint: patients will be assessed at surgery to determine if complete surgical resection was achievable after neo-adjuvant treatment with nivolumab and HF10.

**1.2.5** Assess the safety and tolerability of neoadjuvant nivolumab and HF10 with adjuvant nivolumab in patients with metastatic melanoma.

Endpoint: patients will be monitored for adverse events (AEs) and serious adverse events (SAEs) related to either or both nivolumab and HF10.

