#### Clinical Studies with HF10 + Ipilimumab in unresectable melanoma

# Phase 2 multicenter trial to evaluate efficacy and safety of HF10 oncolytic virus immunotherapy and ipilimumab in patients with unresectable stage IIIB-IV melanoma in the US (Protocol T14-10682, IND No 13,342)

An ongoing phase 2 trial of HF10 and ipilimumab in unresectable metastatic melanoma patients is assessing whether the antitumor effect of HF10 is enhanced by concurrent ipilimumab treatment. Ipilimumab naïve adults with Stage IIIB, IIIC or IV unresectable melanoma with measurable non-visceral lesion(s) received HF10

injections into single or multiple tumors  $(1 \times 10^7 \text{ TCID}_{50}/\text{mL}, \text{ up to } 5 \text{mL/dose}); 4$ injections every week; then up to 15 injections every 3 weeks. Ipilimumab infusions (3 mg/kg) were given every 3 weeks for 4 doses. Tumor responses were assessed at 12, 18, 24, 36, and 48 wks. Best Overall Response Rate (BORR) was determined at 24 wks. Of 46 pts treated, 20% were stage IIIB, 43% stage IIIC, and 37% stage IV. Most HF10-related AEs were  $\leq$  Grade 2, similar to HF10 monotherapy. No DLTs were reported; 3 Grade 4 AEs reported, all not treatment related. 30.4% had Grade 3 AEs. HF10-related Grade 3 AEs (n=3) were left groin pain, thromboembolic event and lymphedema, hypoglycemia, and diarrhea. Twenty-one (46%) patients had received at least 1 prior therapy for metastatic melanoma. Of 43 efficacy evaluable patients, preliminary BORR at 24 weeks per irRC was 41.8% (11.6% CR, 30.2% PR), disease stability rate 67.4% (25.6% SD). Eight responders (53%) were Stage IV. Overall study BORR, including those after 24 weeks, by irRC was 47.7% (15.9% CR, 31.8% PR), disease stability was 65.9% (18.2% SD). In summary, HF10 in combination with ipilimumab treatment does not appear to exacerbate ipilimumab toxicity, is safe, well tolerated and has both local and systemic antitumor activity. The efficacy appears greater than that seen with ipilimumab monotherapy. Since the clinical trial is on-going, the final results of the trial are still pending.

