#### HUNTSMAN CANCER INSTITUTE UNIVERSITY OF LITAH 8 STUDY CALENDAR

Examination	Pre- study 	D0	D7±4 and D21±4	D14±4 and D28±4	D42±4	D56±4 and D70±4	D84±4	Surgery 	Every 4 wks ±2 wks for one year 	EOT  or Progression	Follow- up 
Informed consent	Х										
Medical history	Х										
Concomitant Medications	Х	Х	Х	Х	Х	Х	Х		Х	Х	Х
Eligibility criteria	Х										
Vital signs 	Х	Х	Х	Х	Х	Х	Х		Х	Х	
Height	Х										
Weight	Х	Х		Х	Х	Х	Х		Х	Х	
Physical examination	Х	X 	Х	Х	Х	Х	Х		Х	Х	
Lesion Photography 	Х			Х	Х		Х				
CBC/differential platelet count	Х	X 	Х	Х	Х	Х	Х		Х	Х	
Chemistry 	Х	X 	Х	Х	Х	Х	Х		Х	Х	
Pregnancy Test (serum or urine)	X 	X 					Х		X 		
Thyroid function tests 	X		Х		Х		Х				
PT/INR in patients receiving warfarin anticoagulation therapy	Х	Х	X	Х	Х	Х	X				
LDH	X						X			Х	
Genomic testing 	Х										
Adverse Event Assessment 		Х	Х	Х	Х	Х	Х	Х	Х	Х	Х
Radiologic Evaluation 	Х						Х		X 	Х	
irRC 	Х						Х				
RECIST 1.1 	Х						Х				
Biopsy for correlative studies 		Х			Х			Х		Х	
Blood for correlative studies 		Х	Х	Х	Х	Х	Х		Х		
Nivolumab		Х		Х	Х	Х	Х		Х		
HF10 injections		Х	Х	Х	Х	Х	Х				
Surgery								X 			

Protocol name: Phase II Neoadjuvant trial of Nivolumab in Combination with HF10 Oncolytic Viral Therapy in Resectable Stage IIIB, IIIc, IVM1a Melanoma (Neo-NivoHF10) Version Date: 22JUL2019 Principal Investigator: [name]

Study visits during neoadjuvant nivolumab are scheduled in days. Windows are  $\pm$  business days.

- 1 ALL Pre-study/Screening procedures should be completed within 28 days of study enrollment
- 2. Does not need to be done if occurred 7 days before D0.
- 3. Includes temperature, blood pressure, and pulse rate.
- 4. Chemistry includes: Albumin, Alkaline Phosphatase, Aspartate Aminotransferase (AST), Alanine Aminotransferase (ALT), Total Bilirubin, Calcium, Carbon Dioxide, Creatinine, Chloride, Glucose, Potassium, Protein, Sodium, Urea Nitrogen. Fasting Glucose will be tested as clinically indicated.
- 5. A scan of the chest abdomen and pelvis with extension to the extremities if applicable. The same method (CT scans or possibly PET/CT scan) should be used for all assessments.

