6. Biopsies are mandatory at day 0 and surgery. Biopsies are optional at day 42 and progression. See section 13.1 for details about the collection.

7. Adverse events will be followed until resolution while the patient remains on treatment. Events will be followed for 90 post treatment for SAEs and events thought to be related to the study medication will be followed until resolution or stabilization of the adverse event, or until the patient starts a new treatment regimen.

8. Surgery should occur no later than 28 days after D84.

9. Adjuvant nivolumab should be initiated within 90 days after definitive surgery.

10. EOT visit should occur 28 days (+-14 days) after the completion of therapy.

11. Follow-up should occur every three months (+-or 14 days) for 1 years post EOT visit.

12. Surgery will reset the scan schedule and should occur approximately every 12 weeks after surgery as standard of care.

13. Pathology at surgery will be used to determine pathological response.

14. Collection of blood samples for correlatives is optional and will be collected prior to HF10 injection during the neo-adjuvant (days 0,7, 14, 21, 28, 42, 56, 70, 84) and prior to nivolumab infusion during the adjuvant nivolumab administration.

15. Men and women of childbearing potential must agree to use adequate contraception from the time of consent through 7 months after nivolumab study treatment (neoadjuvant and adjuvant). A pregnancy test will be conducted w/in 72 hours prior to beginning adjuvant nivolumab.

16. Next generation sequeencing is required at screening as per standard of care. Testing will include, but is not limited to BRAF mutational analysis.

17. Thyroid Tests will include TSH and free T4. In the event of hypo/hyper thyroidism, appropriate support will be provided in accordance with institutional guidelines.

18. Lesion photography should be completed at each time point AND when a new lesion is identified.

19. irRC and RECIST should be done prior to surgery. Only RECIST will be used as clinical response criteria and used to make treatment decisions

Protocol name: Phase II Neoadjuvant trial of Nivolumab in Combination with HF10 Oncolytic Viral Therapy in Resectable Stage IIIB, IIIc, IVM1a Melanoma (Neo-NivoHF10) Version Date: 22JUL2019 Principal Investigator: [name]

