# Documentation of "Target" and "Non-Target" Lesions

- All measurable lesions up to a maximum of two lesions per organ and five lesions in total, representative of all involved organs should be identified as *target lesions* and recorded and measured at baseline.
- Target lesions should be selected on the basis of their size (lesions with the longest diameter) and their suitability for accurate repeated measurements (either by imaging techniques or clinical assessments).
- A sum of the LD for *all target lesions* will be calculated and reported as the baseline sum LD. The baseline sum LD will be used as the reference by which to characterize the objective tumor response.
- All other lesions (or sites of disease) should be identified as *non-target lesions* and should also be recorded at baseline. Measurements of these lesions are not required, but the presence or absence of each should be noted throughout follow-up.

	Evaluation of target lesions
Complete Response (CR)	Disappearance of all target lesions (Must persist for a minimum of four weeks)
Partial Response (PR)	At least a 30% decrease in the sum of the LD of target lesions, taking as reference the baseline sum LD (Must persist for a minimum of four weeks)
Progressive Disease (PD)	At least a 20% increase in the sum of the LD of target lesions, taking as reference the smallest sum LD recorded since the treatment started or the appearance of one or more new lesions

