# 9.5 irRC and RECIST 1.1 Concordance

Exploratory objectives for this study include review of the concordance between irRC and RECIST 1.1 response assessments. Both irRC and RECIST 1.1 response assessments will be performed at all timepoints prior to surgery.

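### The calendar and Section 9.5 disagree on when RECIST 1.1 and irRC are scored, and endpoint 1.2.3 has no denominator, so the pre-surgical response rate can be overstated

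*Combined protocol and SAP*

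**What the plan says.** Secondary objective 1.2.3 reads: "Assess the response of tumors prior to surgery based on RECIST 1.1". Exploratory objective 1.3.2 compares irRC with RECIST 1.1.

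The documents give the timing of these assessments in three places:

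- **Section 8, calendar.** The RECIST 1.1 and irRC rows are marked at pre-study and D84 only. The row "Radiologic Evaluation" is also marked during the adjuvant phase and in the EOT or Progression column.
- **Section 8, footnote 19.** "irRC and RECIST should be done prior to surgery", with no day given. It continues: "Only RECIST will be used as clinical response criteria and used to make treatment decisions".
- **Section 9.5.** "Both irRC and RECIST 1.1 response assessments will be performed at all timepoints prior to surgery".

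On scoring, Section 9.4 says: "The best overall response is the best response observed until progression/recurrence and is determined as indicated in the table below". The outcomes in that table are CR, PR, SD and PD. There is no not-evaluable category. For CR and PR the target-lesion table adds: "Must persist for a minimum of four weeks".

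On who counts, Section 4.2 limits evaluability to patients who receive the combination and have surgery. It makes those who leave earlier non-evaluable, with replacement at the principal investigator's discretion. Section 6.1.2 says the same of patients who cannot go to surgery. Section 9.1 has a similar rule, but ties it to pathologic response. Section 10 covers pathologic response, RFS, OS, safety and the exploratory endpoints. It gives no estimator, denominator or missing-data rule for 1.2.3.

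**The concern.** Consider a patient who progresses or stops treatment between D0 and D84. On the calendar alone, this patient has a scan at the EOT or Progression visit and no scheduled RECIST 1.1 or irRC score. On Section 9.5, the same patient should be scored. Two sites, or two analysts, could treat the patient differently and each point to the protocol.

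The gap matters because of what follows it. With no denominator for 1.2.3, the natural fallback is the evaluable set of Sections 4.2 and 6.1.2, which leaves out anyone who did not reach surgery and lets them be replaced. Patients who fail early are mostly non-responders, so removing them raises the reported rate.

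The concordance analysis is exposed too. In Section 9.4 any new lesion is PD. In Section 9.5, irRC adds new measurable lesions to the tumor burden and asks for a rise of at least 25% from nadir, confirmed at least 4 weeks later. Progression is therefore where the two definitions differ most, and early progressors are the patients who may be absent.

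**Working it through.** **1. The plan's own figures.** The documents state no figure for 1.2.3. The only design figures are for the primary endpoint in Section 10: 20 evaluable patients, a null rate of 5%, and rejection at 4 or more responses. With X binomial(20, p):

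- P(X ≥ 4 | p = 0.05) = 0.0159
- P(X ≥ 4 | p = 0.20) = 0.5886 (plan: 59%)
- P(X ≥ 4 | p = 0.30) = 0.8929 (plan: 89%)

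Both powers reproduce. They concern pathologic response, and nothing in this point changes them.

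**2. What the text gives an early leaver.**

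| Situation before D84 | Calendar | Section 9.5 | Row in the best-response table |
|---|---|---|---|
| Progression, scored | not marked | required | PD |
| Progression, scanned but not scored | allowed | not allowed | none |
| Leaves with no post-baseline assessment | no score | silent | none |

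The second line is the conflict, and the third is the missing category.

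**3. Size, as an illustration.** The documents give no rate of leaving before D84, so the number of leavers k is assumed to be 1 to 5. The number of responders r is assumed to be 6 of 20. That is 30%, the same as the expected pathologic response in Section 10, used here only as a convenient figure. The k leavers are taken to be non-responders.

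- No replacement: 20 treated and 20 − k scored. Reported r/(20 − k), against r/20 over all treated.
- Replacement: 20 scored and 20 + k treated. Reported r/20, against r/(20 + k) over all treated.

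| k | No replacement: reported (all treated 30.0%) | Replacement: all treated (reported 30.0%) |
|---|---|---|
| 1 | 6/19 = 31.6% | 6/21 = 28.6% |
| 2 | 6/18 = 33.3% | 6/22 = 27.3% |
| 3 | 6/17 = 35.3% | 6/23 = 26.1% |
| 4 | 6/16 = 37.5% | 6/24 = 25.0% |
| 5 | 6/15 = 40.0% | 6/25 = 24.0% |

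Varying r from 4 to 8, the smallest gap is 4/20 − 4/21 = 1.0 point and the largest is 8/15 − 8/20 = 13.3 points. The gap is zero if k = 0 or if leavers stay in the denominator.

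**4. A rule that acts the other way.** CR and PR must last four weeks. D84 is the only marked post-baseline assessment, and footnote 8 puts surgery no later than 28 days after it, which is exactly four weeks. On the marked assessments alone, few or no responses could be confirmed before surgery.

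**The case against.** A reader might infer that early progressors are scanned but never scored, and that the response rate is therefore overstated. The documents do not support that. Section 9.5 calls for both criteria throughout the pre-surgical period, and Section 9.4 speaks of ongoing evaluation. Footnote 19 makes RECIST the basis for treatment decisions, so calling progression already implies a RECIST judgement. A scored early progressor has a category: three rows of the table lead to PD. Response may also be judged by physical examination, which is marked at every neoadjuvant visit. The missing calendar marks may only reflect that the EOT or Progression column mostly serves visits after surgery. All of this stands. It reduces the scheduling point to a conflict between passages, and the missing category to patients with no post-baseline assessment.

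The overstatement is also conditional. No passage removes early leavers from 1.2.3 by name, and Section 4.2 introduces its rule next to the primary endpoint. But that rule is worded generally and nothing else fills the gap. If it governs 1.2.3, the exclusion comes from Section 4.2 and extra calendar marks alone would not cure it. That also stands, and it is why the denominator has to be stated.

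A reader might also derive a dropout range from the background data. The HF10 plus ipilimumab trial reports "disease stability rate 67.4% (25.6% SD"), leaving 32.6% without stable disease or better, and the nivolumab phase 1 study had 14.8% Grade 3-4 drug-related events. Neither measures leaving before D84. The first is a 24-week result with another checkpoint inhibitor in unresectable disease. The second is an event rate, not a discontinuation rate. Progression is not a listed withdrawal reason in Section 6.5, and Section 6.1.2 lets patients who cannot have surgery stay on treatment.

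**Conclusion.** The point holds in this form: the timing passages conflict, patients with no post-baseline assessment have no category, and endpoint 1.2.3 has no denominator of its own. The pre-surgical response rate can be overstated, and early progressors can drop out of the concordance analysis. Whether this happens depends on how the gaps are filled.

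Under the stated assumptions (6 responders, 1 to 5 non-responding leavers), the overstatement is 1.6 to 10.0 points without replacement and 1.4 to 6.0 points with it. For scale, the exact 95% interval for 6/20 runs from 11.9% to 54.3%. The shift lies within the sampling error of so small a trial, but it is systematic and avoidable.

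The net direction for the reported rate is not fixed, because the four-week persistence rule could lower it. That is a separate gap and does not supply a denominator. Endpoint 1.2.3 is secondary with no hypothesis test, and 1.3.2 is exploratory and descriptive.

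**What to change.** - **Calendar, footnote 19 and Section 9.5:** reconcile them by marking RECIST 1.1 and irRC in the EOT or Progression column when that visit falls before surgery. Score the scan already scheduled there. Where no later scan exists, record irPD as unconfirmed.
- **Sections 9.4 and 10:** state that 1.2.3 is computed over all patients who start neoadjuvant treatment, irrespective of the evaluability rule in Section 4.2. Count a best response of PD, or no post-baseline assessment, as non-response, and show the latter as its own not-evaluable category.
- **Section 9.4 and footnote 8:** reconcile the four-week persistence rule for CR and PR with the 28-day limit from D84 to surgery, so that it is clear what counts as a response in 1.2.3.

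The first two changes cost two calendar marks and a sentence in each of two sections, with no added imaging. The response rate becomes slightly less favourable, and some irRC progressions will stay unconfirmed. The primary test, its sample size and its power do not change.

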# 9.5 irRC and RECIST 1.1 Concordance

Exploratory objectives for this study include review of the concordance between irRC and RECIST 1.1 response assessments. Both irRC and RECIST 1.1 response assessments will be performed at all timepoints prior to surgery.

# Immune-Related Response Criteria (irRC)

Clinical response assessments will be performed according to irRC (Wolchok, 2009)

Table 1: Overall Response using irRC:

Response Assessment	Description	
irCR	Complete disappearance of all lesions (whether measurable or not, and no new lesions)	
	Confirmation by repeat, consecutive assessment $\geq$ 4 weeks after first documentation.	
irPR	Decrease in tumor burden ≥50% relative to baseline	
	Confirmed by a consecutive assessment $\geq$ 4 weeks after first documentation.	
irSD	Not meeting criteria for irCR or irPR, in absence of irPD. A change in tumor burden of neither 50% decrease from baseline nor 25% increase from nadir can be determined.	
irPD	Increase in tumor burden ≥25% relative to nadir (minimum recorded tumor burden)	
	Confirmation by a repeat, consecutive assessment $\geq 4$ weeks after the first documentation.	

Abbreviations: CR= Complete Response; irRC= Immune-Related Response Criteria; PD= Progressive Disease; PR=Partial Response; SD=Stable Disease

Measurable Response	Non-measurable response		
Target and new, measurable lesions % change in tumor burden	Non-target lesions	New non- measurable lesions	Overall irRC Response
$\downarrow 100^{1}$	Absent	Absent	irCR 
↓ 100 	Stable	Any	irPR 
↓ 100 	Unequivocal progression	Any	irPR 
$\downarrow \ge 50^1$	Absent or Stable	Any	irPR 
$\downarrow \ge 50^1$	Unequivocal progression	Any	irPR 

Table 2: Derivation of irRC overall responses

Protocol name: Phase II Neoadjuvant trial of Nivolumab in Combination with HF10 Oncolytic Viral Therapy in Resectable Stage IIIB, IIIc, IVM1a Melanoma (Neo-NivoHF10) Version Date: 22JUL2019 Principal Investigator: [name]

$\downarrow \ge 50 \text{ to } \uparrow < 25^1$	Absent or Stable	Any	irSD
$\downarrow \ge 50$ to $\uparrow < 25^1$	Unequivocal Progression	Any	irSD
$\uparrow \ge 25^2$	Any	Any	irPD 

Decrease relative to baseline

 Increase relative to nadir

 confirmed by consecutive scan  $\geq$ 4 weeks after first documentation

## 9.6 **Overall Survival**

Patient survival will be collected for up to one year following the EOT visit. Survival will be calculated by the Kaplan-Meier method.

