# 6.1.3 Adjuvant treatment

#### Nivolumab

Adjuvant nivolumab should be initiated within 90 days after definitive surgery. Nivolumab will be administered at a flat dose of 480 mg IV every 28 days (every 4 weeks) for one year. We have chosen the 480mg IV dose every 4 weeks in accordance with the application made by Bristol-Myers Squibb to the FDA on July 24, 2017. This dose will be similar to the current FDA approved dose of 240 mg IV every 2 weeks with fewer infusions for the patient.

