# **10 STATISTICAL CONSIDERATIONS**

The primary endpoint of pathologic response including pCR is expected to be seen in 30% of patients, hence 6 of the planned 20 patients are expected to have a pathologic response, including pCR.

Pathological response will be determined by assessing the tumor viability at baseline and at surgery. Samples will be scored as a percentage viability (0-100%). A pathologic complete response (pCR) will be defined as no viable residual melanoma cells in the surgical specimen. A major pathologic response will be defined as <50% viable tumor cells. A minor pathologic response will be defined as 50% or greater viable tumor cells, including specimens that have 100% viability at surgery. Pathologic response rate (pRR) will be defined as frequency of either pCR or a major pathologic response. Analysis will also be performed of baseline tumor biopsies and on treatment biopsies if available for comparisons with the surgical resection specimen.

The null hypothesis is that the pathologic response rate for patients receiving the treatment is 5% or less. The alternative hypothesis is that the pathologic response rate is 30%. With 20 evaluable patients there will be 59% power using an exact binomial test at the one-side 0.05 significance level if the true response rate is 20%, and 89% power at one-sided alpha = 0.05 if the true response rate is 30%. Four or more pathologic responses in up to 20 patients will be sufficient to reject the null hypothesis. In additional to the statistical test, a 95% exact binomial confidence interval for the pathologic response rate will be calculated.

Kaplan-Meier methods and associated confidence intervals will be used to analyze RFS and OS. All subjects assessed for relapse will contribute to this analysis.

The statistical analysis of the safety data will be descriptive and tabular in nature.

The statistical analysis of pathologic and correlative exploratory endpoints will be descriptive. No hypothesis tests will be performed for exploratory endpoints.

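### Overall-survival follow-up is tied to the end-of-treatment visit, so early stoppers are censored before completers; late Kaplan-Meier survival is likely too high if stopping is prognostic

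*Combined protocol and SAP*

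**What the plan says.** Three places set the length of survival follow-up.

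- Section 9.6: "Patient survival will be collected for up to one year following the EOT visit".
- Section 8, calendar notes 10 and 11: "EOT visit should occur 28 days (+-14 days) after the completion of therapy", and "Follow-up should occur every three months (+-or 14 days) for 1 years post EOT visit".
- Section 1.2.2 uses a different anchor: "patients will be followed for survival for one year after completion of adjuvant nivolumab".

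Section 10 names the estimator: "Kaplan-Meier methods and associated confidence intervals will be used to analyze RFS and OS". It adds that the subjects contributing are those assessed for relapse. No section gives a time origin for overall survival (OS), a censoring rule, or a common date or duration to which all patients are followed. Sections 4.2 and 6.1.2 treat patients who do not reach surgery as non-evaluable and replaceable, without saying whether they are still followed for survival.

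**The concern.** Kaplan-Meier estimation requires that, at any given time, patients who are censored have the same prospects as those who remain under observation. A follow-up window that starts when treatment stops can break this. A patient who stops because of recurrence has an early EOT visit and leaves the risk set early, while a patient who is doing well is followed through a year of adjuvant treatment and a further year. If the early leavers then die at a higher rate, those deaths go unrecorded and the later part of the curve is too high.

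The plan makes such a link plausible without requiring it. The calendar pairs end of treatment with progression in a single column, note 19 has RECIST feed into treatment decisions, and Section 6.5 lists performance-status decline and intercurrent illness as possible withdrawal reasons. Section 6.5 does not list progression.

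Separately, the Section 1.2.2 window has no defined start for a patient who never starts or never completes adjuvant nivolumab, and so conflicts with Section 9.6 for that patient.

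**Working it through.** The plan states no OS rate, event count or precision, so there is no plan figure to reproduce. The check is calendar arithmetic, followed by bias calculations on stated assumptions.

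**Inputs from the documents**
- Section 8, note 8: "Surgery should occur no later than 28 days after D84", so surgery falls at day 84 to 112.
- Section 8, note 9: "Adjuvant nivolumab should be initiated within 90 days after definitive surgery", so adjuvant start is 0 to 90 days after surgery.
- Section 6.1.3: "Nivolumab will be administered at a flat dose of 480 mg IV every 28 days (every 4 weeks) for one year". I take the last dose as 336 to 364 days after the first adjuvant dose.
- EOT is 28 days after therapy ends (the 14-day window is ignored), with 365 days of follow-up after it.

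**Step 1. End of OS follow-up, counted from day 0**

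End of follow-up = day treatment stops + 28 + 365, divided by 30.44 for months.

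- Earliest completer: 84 + 0 + 336 = day 420; 420 + 393 = day 813, month 26.7.
- Latest completer: 112 + 90 + 364 = day 566; 566 + 393 = day 959, month 31.5.

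| Treatment stops | Follow-up ends (month) | Shortfall against completers (months) |
|---|---|---|
| Day 42 | 435 d = 14.3 | 12.4 to 17.2 |
| Day 84, no adjuvant | 477 d = 15.7 | 11.0 to 15.8 |
| Adjuvant month 3 | 18.7 to 22.5 | 8 to 9 |
| Adjuvant month 6 | 21.7 to 25.5 | 5 to 6 |
| Adjuvant month 9 | 24.6 to 28.5 | 2 to 3 |

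In the last three rows the earliest and latest stops are each compared with the completer on the same calendar. A stop at day 28 ends follow-up at month 13.8, so in practice bias cannot appear before about month 14. The extreme case, a stop after the first dose alone, gives 393 days, month 12.9.

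**Step 2. Bias if early stoppers form a poor-prognosis group (assumed)**

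Let a fraction p stop early, all censored at month c, with exponential survival in both groups. For t > c:

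KM(t) = S_mix(c) × S_rest(t) / S_rest(c), compared with the true S_mix(t).

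Example: p = 30%, medians 18 months (early stoppers) and 96 months (the rest), c = 15, t = 24.
- S_mix(15) = 0.3 × 0.561 + 0.7 × 0.897 = 0.797
- S_rest(24)/S_rest(15) = 0.937, so KM(24) = 0.746
- True S_mix(24) = 0.3 × 0.397 + 0.7 × 0.841 = 0.708
- Excess: 3.9 points

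For p of 20% to 40%, early-stopper medians of 12 to 24 months and medians of 60 to 96 months for the rest, the excess at 24 months is:
- c = 15 (every stop before adjuvant therapy): 1.7 to 5.8 points
- c = 20: 0.7 to 2.2 points
- c = 22: 0.4 to 1.1 points
- c = 24: 0

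**Step 3. Bias if treatment stops at recurrence (assumed)**

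Simulation with 400,000 patients per scenario. Assumptions: 12-month recurrence risk 20% to 40%; median survival after recurrence 12 to 36 months; 0 or 20% additional stops for toxicity unrelated to prognosis; treatment otherwise ends at month 17; follow-up ends 12.9 months after stopping. Excess over true OS: about 0 at 18 months, 0.6 to 1.6 points at 24 months, and 1.2 to 3.2 points at 28 months.

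Section 2.1 cites recurrence of up to 60% at 18 months after resection. With a constant hazard that is 1 − 0.4^(12/18) = 46% at 12 months, slightly above the assumed range, but it is historical and not for this regimen.

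**Step 4. Control case**

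With 30% of patients stopping at random times unrelated to prognosis, the Kaplan-Meier limit equals the truth at 18, 24 and 28 months (84.7%, 80.1%, 77.2%).

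**Step 5. Sampling error**

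In the Step 3 model with 20 patients (30% recurrence, 24-month median after recurrence, 20% toxicity stops), the standard deviation of the 28-month estimate is about 8 points. Without censoring, the standard error near 71% survival is √(0.708 × 0.292 / 20) = 10 points.

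**The case against.** The strongest reply is that the effect is conditional, small, and confined to a descriptive secondary endpoint. Much of this stands. OS has no hypothesis test, event target or landmark time, and every excess above is smaller than the sampling error. Stops for toxicity are not shown to be prognostic, and Section 6.5 does not make progression a reason to stop.

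It is also fair that the largest gaps belong to patients who stop before surgery, and Sections 4.2, 6.1.2 and 10 leave it unclear whether they enter the OS analysis at all. Leaving them out would not rescue the estimate, however. It would replace a censoring problem with a selection problem, which also pushes OS upward if those patients did poorly.

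Three stronger readings are tempting, and the documents do not support them.
- A reader might infer that OS is certainly biased upward. That needs stopping to predict death, which the plan makes plausible but does not establish.
- A reader might infer that beyond month 15 the curve rests almost only on completers. The Step 1 table contradicts this: patients who stop partway through adjuvant treatment stay under observation to about month 19 to 28.
- A reader might infer from Section 1.2.2 that a patient who never starts adjuvant nivolumab gets no survival follow-up. Section 9.6 and note 11 give a year after EOT without that restriction, so this is a conflict of wording and not an absence of follow-up.

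What the reply does not answer is that a confidence interval reflects sampling error and not censoring bias, and that vital status never collected cannot be recovered at analysis.

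**Conclusion.** The point holds in conditional form. As written, the plan makes OS censoring depend on when treatment stops. The shortfall in follow-up is about 11 to 17 months for stops before or around the start of adjuvant nivolumab and falls to 2 to 3 months by adjuvant month 9. If stopping is linked to recurrence or poor prognosis, the Kaplan-Meier estimate after about month 14 is likely too high: by roughly 0.5 to 2 points at 24 months when most stops occur during adjuvant therapy, and by up to about 6 points if all occur before it. These sizes rest wholly on assumed survival and recurrence rates, because the documents give none. The primary pathologic-response result is untouched. The conflict between Sections 1.2.2 and 9.6 needs reconciling whatever the size of the bias. This is a cheap improvement and not a threat to the trial's main conclusion.

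**What to change.** In Sections 1.2.2 and 9.6 and calendar note 11, collect vital status for every treated patient, including those who stop before surgery, to one fixed time from first dose, whenever treatment stopped. A natural choice is the time by which completers finish follow-up, about 27 to 32 months. In Section 10, define OS from first dose, name the analysis set as all treated patients, and censor only at the date last known alive or at the fixed time. Use one anchor in place of the two now in Sections 1.2.2 and 9.6.

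A fixed duration is preferable to a cut-off at the last patient's final visit. Such a cut-off would also lengthen follow-up for completers who enrolled early, by up to the 15-month enrollment period.

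The cost is protocol wording plus a few vital-status contacts or chart checks for early stoppers, with no added visits or procedures. A time at the upper end of the range would also add up to about 5 months of vital-status checks for the fastest completers (31.5 − 26.7 = 4.8).

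Section 4.4 should be checked at the same time. If its 3 years include the 15 months of enrollment, the last patient has only 36 − 15 = 21 months, which is already less than completers need under the present schedule. The text does not say which reading applies.
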